2.1 Shoulder Arthroplasty Background

Shoulder replacement surgery started in the 1950's in the United States primarily to treat severe shoulder fractures. Today, shoulder arthroplasty is used to treat many painful conditions of the shoulder such as; degenerative joint disease (Osteoarthritis), Rheumatoid Arthritis, post-traumatic arthritis and avascular necrosis. The most common reason for undergoing shoulder replacement surgery is osteoarthritis. Osteoarthritis, known as a degenerative disease of the shoulder, is characterized by permanent loss of the normal surface of the ball and socket of the shoulder joint. The cartilage that normally provides this smooth surface, known as articular cartilage, degenerates and wears down. This causes loss of comfort and function of the shoulder (pain, weakness, stiffness and grinding). When the symptoms of shoulder arthritis are severe, shoulder joint replacement arthroplasty may be considered. Osteoarthritis most often occurs in people over 50. In younger people, it can result from injury or trauma, such as a fractured or dislocated shoulder, known as posttraumatic arthritis. Shoulder arthritis can also be caused by conditions where blood circulation to the ball and socket is disrupted, such as avascular necrosis. Another common type of shoulder arthritis is rheumatoid arthritis. Rheumatoid arthritis is a systemic condition that causes inflammation of the lining of the joints. This inflammation can, over time, invade and destroy the cartilage and bone.

A person with shoulder arthritis will likely have pain while moving the shoulder as well as after moving the shoulder. Shoulder arthritis is diagnosed by a history of lost shoulder function (often without injury), or during physical exam, where there is stiffness and grinding on movement and a characteristic appearance during X-ray, where the humeral head can be seen contacting the socket without the normal space occupied by the articular cartilage.

2.2 Treatment Options: Total Shoulder Arthroplasty

There are many types of shoulder replacements available today. The purpose of this trial will be to demonstrate the safety and performance of ArthroX's Eclipse™ Total Shoulder Prosthesis.

A Total Shoulder Arthroplasty has the same basic parts; a humeral component and a glenoid component. The humeral component evolved through several generations over the years. The 1st generation "Monoblock", consisted of a single piece, that could not move and had limited sizes. The second generation, "Modular" had independent segments for the head and stem, which therefore could be interchanged and sized for the patient. The third generation, "Anatomical", allows for adjustment of the prosthetic humeral head position in reference to the head and some allow for various degrees of head inclination. The traditional glenoid component is an all-polyethylene implant with a slightly convex backside and a keel to be inserted in the glenoid space. More currently used glenoid components have their keels replaced by two or more pegs. In this trial both glenoid components will be available for either treatment group.

2.3 Investigational Device: Eclipse™ Shoulder Prosthesis

The ArthroX Eclipse™ Shoulder Prosthesis is a unique stem free humeral joint prosthesis that is designed as a humeral replacement device. The Eclipse has three design elements 1) a cobalt chrome humeral head, 2) a titanium plasma spray (TPS) and Calcium phosphate (CaP) coated titanium trunion and 3) a titanium hollow screw. The Eclipse is unique in that it strikes a balance between conventional resurfacing devices and standard stemmed devices with several key advantages such as:

- Humeral head can be positioned independently of the humeral shaft axis, which is especially important in post-traumatic arthritis situations;
- Anatomic reconstruction of the humeral head, as the prosthesis can be adjusted to the cortical rim of the humeral resection at the anatomical neck;
- Nine anatomic head diameters available in 2 mm increments;
- Fenestrated cage screw for enhanced fixation;
- Multiple cage screw lengths account for anatomical variations;
- Unrestricted approach to the glenoid;
- Simplified revision arthroplasty and avoidance of complications associated with humeral shaft osteotomy; and
- Potential for less invasive exposure.

2.3.1 Target Indication for Use

The Arthrex Eclipse Shoulder Prosthesis is indicated as a total joint replacement where the humeral head and neck are of sufficient bone stock and the rotator cuff is intact or re-constructible for the following indications; osteoarthritis, avascular necrosis, post-traumatic arthritis, or rheumatoid arthritis.

This product has CE marking and is Canadian licensed, but does not have FDA clearance in the United States.

2.4 Control Device: Univers™ II Shoulder Prosthesis

The Univers™ II Shoulder Prosthesis humeral component was designed to account for anatomical variation of the proximal humerus commonly encountered by the surgeon. Variable adjustment with respect to the inclination angle, version and head offset are features critical to the reconstruction of the proximal humerus. The simplified design of the Univers™ II Shoulder Prosthesis humeral component allows the surgeon to adapt the humeral stem and articular surface to the position that best represents the patient's normal anatomy. All the adjustments can be made intraoperatively with the implant in the humeral canal. The Arthrex Univers™ II Shoulder Prosthesis consists of a titanium alloy stem for attachment to the humerus, a Chromium-Cobalt spherical head for replacing the humeral head and a titanium trunion construct to connect the stem to the head. The Univers™ II Shoulder Prosthesis has multiple head diameters and heights, along with multiple keeled and pegged glenoid options.

2.4.1 Indication for Use

The Univers™ II Shoulder Prosthesis is indicated in shoulder replacement when conditions indicating severe pain or significant disability resulting from one or more of the following conditions:

- degenerative, rheumatoid, post-traumatic disease
- injury of the glenohumeral joint
- non-union head fracture of long duration
- irreducible 2 and 4 part proximal humeral fractures
- avascular necrosis of the humeral head
- difficult clinical management problem where arthrodesis or resectional arthroplasty is not acceptable.

This product has CE marking, is Canadian licensed and FDA cleared in 510(k) K071032, K010124, K083435 and K120044.

3 Study Design, Objectives and Endpoints

3.1 Study Design

Prospective, randomized, multi-center, clinical study. Up to twenty centers will randomize up to 350 subjects who are candidates for a Total Shoulder Arthroplasty, to 2 treatment groups in a 2:1 (Eclipse: Univers II) fashion. FDA has agreed that randomization of controls may be halted after N=77, with continuing enrollment of Eclipse until the originally planned Eclipse sample size target is reached. Given the timing needed for approval to stop control enrollment, the actually number of evaluable randomized controls may be slightly larger. This study will cease enrollment and be terminated if the Eclipse Shoulder Prosthesis receives 510 (k) clearance prior to all subjects completing the study.

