4.1 Study Population

4.1.1 Intention to Treat (ITT) Cohort

The investigator will invite prospective patients to enroll in the study that meet the inclusion/exclusion criteria and have signed the informed consent. All patients randomized to either the investigational device (ArthroX Eclipse™ Shoulder Prosthesis) or the control device (ArthroX Univers™ II Shoulder Prosthesis) will be included in the ITT cohort. Randomization will take place after patients have been screened for inclusion and exclusion criteria. Patients found prior to randomization to not meet all inclusion and exclusion criteria will be defined as screen failures and will not receive the investigational device. These patients will be excluded from the ITT cohort.

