4.1.2 Per Protocol (Efficacy Evaluable) Cohort

Patients included in the ITT cohort but found to have been randomized in error will be excluded from the Per Protocol (Efficacy Evaluable) cohort. A patient will be considered to have been randomized in error if it is determined that the patient has clinically significant violations of the inclusion or exclusion criteria. Because approval and labeling is sought for patients meeting study inclusion and exclusion criteria, primary non-inferiority testing will be conducted in the Per Protocol (Efficacy Evaluable) cohort. Safety endpoints will be summarized for the Per Protocol cohort for the same reason. However, all adverse events that occur in the study will be reported in safety listings based on the ITT cohort.

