10.4 Sample Size Analysis for Primary Non-Inferiority Test

Given the above criteria, the Sponsor expects a success rate of 88% for both the Eclipse and control group.

To determine the required sample size, it was assumed that the above primary hypotheses will be tested using 1-sided $\alpha=0.05$ at a statistical power of at least 80%. Under these assumptions, nQuery Advisor 7.0 module PTE0U-1 produces the following:

“When the sample sizes in the groups are 98 and 196, a two-group large-sample normal approximation test of proportions with a one-sided 0.05 significance level will have 80% power to reject the null hypothesis that the test and the standard are not equivalent (the difference in proportions, $p_T - p_S$, is -0.10 or farther from zero in the same direction) in favor of the alternative hypothesis that the proportions in the two groups are equivalent, assuming that the expected difference in proportions is 0.00 and the proportion in the standard group is 0.88.

Therefore, the total number of Per Protocol (Efficacy Evaluable) patients required under these assumptions are $N=294$. The number of protocol violations of inclusion / exclusion criteria (i.e., randomized in error) is expected to be small. The randomized sample size is adjusted up by 15% to account for both loss-to-follow-up and exclusions due to protocol violation to $N=347$.

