10.7.2 Adverse event detail listings

Adverse events listings will be provided for all patients in the ITT cohort and will provide details regarding adverse event type, relation to shoulder procedure, action taken, and clinical outcome. Separate listings will be constructed for adverse events with “definite” relationship to the device, “severe” adverse event, “severe device-related”, serious adverse events, and for all adverse events. The listing for all adverse events will be sorted by adverse event type.

Additional listings will be provided that include all adverse events among procedures requiring revision, removal, or replacement and all adverse events among patients who died.

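### Section 10.4 still claims 80% power on 98 and 196 patients although section 3.1 lets control randomisation stop after 77, and no cohort definition covers the Eclipse patients enrolled afterwards

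*Combined protocol and SAP*

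**What the plan says.** Section 3.1 describes 2:1 randomisation (Eclipse to Univers II) of up to 350 subjects. It then adds that "FDA has agreed that randomization of controls may be halted after N=77, with continuing enrollment of Eclipse" going on "until the originally planned Eclipse sample size target is reached". The next sentence says that the number of evaluable randomised controls may end slightly above this. It gives no upper limit.

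Section 10.4 gives one calculation, for 98 controls and 196 Eclipse patients, with which "a two-group large-sample normal approximation test of proportions with a one-sided 0.05 significance level will have 80% power". It assumes 88% success in both arms and a margin of 0.10, and arrives at 294 Per Protocol patients, raised to 347 randomised. It contains no calculation for a reduced control arm.

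On cohorts, section 4.1.1 builds ITT from "All patients randomized to either the investigational device" or to the control. Section 4.1.2 forms the Per Protocol cohort by removing from ITT the patients randomised in error, and says that "primary non-inferiority testing will be conducted in the Per Protocol (Efficacy Evaluable) cohort". On safety, section 10.7.2 says: "Adverse events listings will be provided for all patients in the ITT cohort".

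**The concern.** There are two gaps.

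The first is that the power statement describes a design that need not be run. If controls stop at or near 77 with the Eclipse target unchanged, the 98/196 calculation no longer applies.

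The second is that Eclipse patients enrolled after the halt have no control allocation to be randomised against and no concurrent controls. The cohort definitions, read literally, leave them out of ITT and so out of Per Protocol. Section 3.1, however, enrols them in order to reach the planned Eclipse number. Section 10.5 has poolability in its title but covers only baseline group differences and site differences.

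The size and make-up of the primary cohort are therefore open to decision after data are seen. If the late patients are in, any change over time in patient selection, surgical experience or assessment enters the primary difference, and its size and direction are unknown. If they are out, they add nothing to the primary test, and on the same literal reading their adverse events have no specified listing.

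**Working it through.** **Inputs.** From section 10.4: success 0.88 in both arms, one-sided alpha 0.05, normal approximation, 98 controls and 196 Eclipse evaluable, 15% allowance for loss and exclusions. From sections 10.2 and 10.4: margin 0.10. From section 3.1: 2:1 allocation and the halt after 77.

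**Formula.** Power = Φ(0.10 / SE − 1.645), with SE = √[0.88 × 0.12 × (1/nC + 1/nE)].

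**The plan's figure.** At 98/196, SE = 0.0402 and 0.10/SE = 2.487, so power = Φ(0.842) = 80.0%. The stated figure is reproduced.

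**The permitted design.** At 77/196, SE = 0.0437 and 0.10/SE = 2.288, so power = Φ(0.643) = 74.0%. Patients randomised 2:1 before the halt number 77 and 2 × 77 = 154. For these alone SE = 0.0454 and power = Φ(0.560) = 71.2%.

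| Controls / Eclipse (evaluable) | Normal approximation | Exact binomial, Wald test |
|---|---|---|
| 98 / 196 (as planned) | 80.0% | 81.9% |
| 90 / 196 | 78.0% | – |
| 85 / 196 | 76.6% | 78.6% |
| 80 / 196 | 75.0% | – |
| 77 / 196 (late patients pooled) | 74.0% | 77.3% |
| 77 / 154 (concurrent only) | 71.2% | 73.1% |
| 65 / 196 (77 randomised, 15% lost: 77 × 0.85 ≈ 65) | 69.3% | 71.9% |

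**Size of the primary cohort.** Late patients out: 77 + 154 = 231. Late patients in: 77 + 196 = 273. Stated in section 10.4: 294.

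**Non-concurrent share.** Late Eclipse patients = 196 − 2 × nC. This gives 42 (21%) at 77 controls, 36 (18%) at 80 and 26 (13%) at 85.

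**Effect of drift if pooled at 77/196.** The documents give no drift figure, so the values below are assumptions. True control success is 0.88. The 154 early Eclipse patients succeed at 0.78, exactly on the margin, and the 42 late patients at 0.78 plus the drift. Bias in the difference is (42/196) × drift. Type I error is by exact enumeration at one-sided 0.05.

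| Assumed drift (points) | Bias (points) | Type I error |
|---|---|---|
| −10 | −2.1 | 1.5% |
| −5 | −1.1 | 2.6% |
| −2 | −0.4 | 3.5% |
| 0 | 0 | 4.3% |
| +2 | +0.4 | 5.2% |
| +5 | +1.1 | 6.9% |
| +10 | +2.1 | 10.7% |

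With more controls the +10 figure falls, to 9.1% at 80 and 7.8% at 85.

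**The case against.** The 98/196 calculation is correct for its own inputs, and it is where the Eclipse target comes from. The halt is permissive, is recorded as agreed with FDA, and the control count may exceed 77. Lower power is mainly the sponsor's risk and does not bias the test. All of this stands, but none of it supplies the power of the design that section 3.1 permits: at 80, 85 or 90 controls the plan's own method stays below 80%.

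The next sentence of section 3.1 speaks of evaluable controls, so 77 is most naturally an evaluable count. That is fair, and it makes 65/196 the less likely case. The text does not settle the question.

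The loss also depends on the method. Exact power at 77/196 is 77.3%, and a Farrington-Manning variance gives 79.4%. However, Farrington-Manning gives 83.0% at 98/196, so it is not the method behind the stated 80%.

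The evident purpose of enrolling late Eclipse patients is to count them, so pooling is probably intended. That is plausible, but the written definitions say otherwise.

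The adverse event point is the weakest. Section 4.1.2 promises that all adverse events in the study will be reported, but ties those listings to ITT. Loss of safety data is a consequence of the literal wording, not a likely outcome.

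The drift values are hypothetical, and negative drift is conservative. The type I figures also assume one-sided 0.05. Section 10.8 refers to a 95% confidence interval for the primary test. If that is two-sided, the error is 3.3% at +5 and 5.4% at +10, and power is lower (62.9% at 77/196). Section 10.5.1 offers partial protection through its covariate check, but only against measured baseline differences, not period effects.

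**Conclusion.** The concern holds on both parts and should be fixed. Stated power overstates that of the permitted design by about 6 points by the plan's own method (80.0% to 74.0%), or about 5 by exact calculation (81.9% to 77.3%). It falls further if only concurrent patients count. These figures assume that 77 is an evaluable count, that 196 evaluable Eclipse patients are reached, and that the 88% success rates and one-sided 0.05 are kept.

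The plan also leaves open whether the primary test includes up to 42 Eclipse patients with no concurrent control. Whether drift would occur, and in which direction, cannot be judged from the documents. The halt itself is not in question.

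**What to change.** 1. In section 10.4, give power for the design in force: about 74% at 77/196 and about 71% for 77/154 by the plan's method, with the exact values (77.3% and 73.1%) alongside if wished. State whether 77 is a randomised or an evaluable count.
2. In sections 4.1 and 10.2, state which cohort post-halt Eclipse patients belong to and whether they enter the primary test, in agreement with section 3.1. In section 10.7.2, state that their adverse events are listed.
3. If they enter the primary test, pre-specify a non-inferiority analysis in concurrently randomised patients only, reported beside the primary result as a sensitivity analysis.

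The third item should not become a second pass/fail condition: requiring both analyses to succeed would cut exact power from about 77% to about 71% (70.6% by simulation). The concurrent-only analysis has about 3 points less power than pooling by normal approximation and about 4 by exact calculation.

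The cost is wording in four sections and one extra analysis. No more patients are needed. The published power figure becomes less favourable.

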3.2 Objectives and Study Endpoints

3.2.1 Primary Safety and Effectiveness Objective

The primary safety and effectiveness objective for this study is to demonstrate that the proportion of patients expected to achieve a Month 24 Composite Clinical Success (CCS) criterion among patients implanted with the investigational device (ArthroX's Eclipse) is clinically non-inferior to a control device (ArthroX's UniversTM II). The composite clinical success criterion contains the following components:

- Functional improvement as reflected in the Adjusted Constant score change from baseline to the Month 24 clinical visit,
- Radiographic outcome success at Month 24,
- Absence of reoperations and revisions up to the subject's completion of the study, and
- Lack of serious device related complications up to the subject's completion of the study.

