4.2.1 Inclusion Criteria

1. The subject is ≥ 21 years of age
2. The subject has continued symptoms in target shoulder despite at least 3 months of other treatment modalities (e.g.: anti-inflammatory, physical therapy and steroid injections)
3. The subject has a diagnosis in the target shoulder of one or more of the following: osteoarthritis, avascular necrosis, post-traumatic arthritis, or rheumatoid arthritis. The above are defined as follows:

Osteoarthritis (Kellgren-Lawrence Grade 3 or higher), with clinical history of an absence of major trauma to the joint; symptoms of pain, stiffness, swelling and/or loss of motion; and with radiographic evidence of joint space narrowing, sub-chondral sclerosis, peripheral osteophytes with or without posterior subluxation of the humeral head.

Avascular Necrosis (Staging System of Cruess Stage IV or higher), with a clinical history of a known risk factor for avascular necrosis; symptoms of pain and loss of motion; and radiographic findings of flattening or collapse of the humeral head and joint space narrowing.

Post-Traumatic Arthritis (Kellgren-Lawrence Grade 3 or higher), with a clinical history of trauma to the targeted shoulder and subsequent pain, stiffness, swelling and loss of motion; and with radiographic evidence of joint space narrowing, sub-chondral sclerosis, peripheral osteophytes.

Rheumatoid Arthritis (American College of Rheumatology classification score of 6 or higher), with a clinical history that demonstrates: morning stiffness for at least 1 hour and present for at least 6 weeks, swelling, loss of motion, and/or serum rheumatoid factor; and radiographic findings of narrow joint space, peri-articular osteopenia, and/or peri-articular erosions and medial glenoid erosion.

4. The subject presents with pain and functional impairment in the index shoulder, measured by an Adjusted Constant Score of ≤ 50 . Note: The Adjusted Constant Score will be calculated from the raw Constant Score to establish patient eligibility.
5. The subject is willing to receive implantation of the ArthroX™ Shoulder Prosthesis or Uniers™ II Shoulder Prosthesis.
6. The subject must be physically and mentally willing and able to comply with all study procedures (including follow-up visits and radiographic assessments) until the conclusion of the study.
7. The subject has been informed of the nature of the study and provided written consent as approved by the sites local Institutional Review Board or Ethic Review Board.

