10.5 Analysis of Baseline Differences and Poolability

10.5.1 Description of demographics and baseline characteristics

Demographic and baseline characteristics will be tabulated and compared between the investigational group and control group. Variables to be compared will include baseline shoulder assessment, disease severity, age, gender, limb dominance, primary diagnosis, Body Mass Index (BMI), weight, and height. Descriptive p-values will be determined using Wilcoxon rank sum tests for continuous measures and chi-square or exact tests for categorical variables. However, focus will be on clinical significance of group differences and only secondarily on p-values, since these p-values are not associated with planned comparison. If there are clinically significant group differences for any baseline variable, then multiple logistic regression will be used to assess the impact of controlling for the baseline variable on conclusion. Specifically, the odds ratio for achieving Month 24 CCS

comparing investigational group to control group will be computed with and without including the baseline variable in question. If the odds ratio changes by less than 15%, it will be concluded that the primary results are not confounding by device group imbalance for that variable (Mickey RM, 1989).

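### The primary CCS comparison makes no fixed use of the baseline Adjusted Constant Score, and Section 10.5.1 allows adjustment only after an imbalance is seen and only on the odds-ratio scale

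*Combined protocol and SAP*

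**What the plan says.** **Endpoint.** Section 3.2.1 lists as the first CCS component "Functional improvement as reflected in the Adjusted Constant score change from baseline to the Month 24 clinical visit". Section 3.2.2 requires a gain of at least 10 points and a final score of at least 54.

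**Availability.** Section 4.2.1 requires a baseline score of 50 or below and notes: "The Adjusted Constant Score will be calculated from the raw Constant Score to establish patient eligibility". Baseline is therefore known before randomisation for every eligible patient.

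**Primary comparison.** Section 10.2 (Primary Efficacy Hypothesis) states the hypotheses as a difference in CCS proportions with margin 0.10. Section 10.4 sizes the trial with "a two-group large-sample normal approximation test of proportions with a one-sided 0.05 significance level". Neither names a covariate or stratification factor. No separate paragraph names the primary test, so its unadjusted form is inferred from these two sections; nothing in the plan points the other way.

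**Role of baseline variables.** Section 10.5.1 compares the arms on a list that begins with the baseline shoulder assessment. It continues: "If there are clinically significant group differences for any baseline variable, then multiple logistic regression will be used to assess the impact". The odds ratios with and without the variable are then compared. A change below 15% is read as no confounding. The section does not say what follows from a larger change.

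**The concern.** A complete pre-randomisation measurement that enters the endpoint definition is an obvious candidate covariate, and adjusting for it could tighten the non-inferiority bound without more patients.

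The more practical worry is the rule in Section 10.5.1:

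- The decision to adjust rests on an undefined clinical judgement about differences between arms that have already been seen.
- The check uses an odds ratio, while the margin is a risk difference. An odds-ratio change below 15% does not show whether the lower bound stays above -0.10.
- If the change is 15% or more, no analysis is specified, so the primary conclusion would have no agreed basis.

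**Working it through.** **1. Reproduce the plan's figure.** Inputs from Section 10.4: one-sided 0.05, 80% power, margin ("is -0.10 or farther from zero in the same direction"), control rate ("the proportion in the standard group is 0.88"), true difference ("the expected difference in proportions is 0.00"), allocation 2:1.

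Control n = (1.645 + 0.842)² × 0.88 × 0.12 × (1 + 1/2) / 0.10² = 97.9, so 98 controls and 196 Eclipse. At 15% loss, 98/0.85 and 196/0.85 round up to 116 + 231 = 347. Both stated figures are reproduced by a formula without covariates.

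**2. Unadjusted bound and power.** SE = √[0.88 × 0.12 × (1/nE + 1/nC)]; power = Φ(0.10/SE − 1.645); the one-sided 95% bound lies 1.645 × SE below the estimate.

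- 196/98: SE 0.0402, bound 6.61 points below, power 80.0%.
- 196/77 (Section 3.1 lets control randomisation stop after 77): SE 0.0437, bound 7.19 points below, power 74.0%.

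**3. How far the endpoint rule ties CCS to baseline.** A final score of at least 54 and a gain of at least 10 together mean passing the larger of 54 and baseline + 10. The second is larger only when baseline exceeds 44; a patient starting at 50 needs 60. Entry is capped at 50, so only baselines from 44 to 50 are affected. In the simulation below, that is about 16% of eligible patients, and the 10-point rule alone decides the outcome in about 0.3% or fewer.

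**4. Share of CCS variance explained by baseline (R²).** Baseline was drawn as normal with mean 37.3 and SD 15.6 (Section 10, Table 3) and kept within 0-50. The Month 24 score was drawn as normal with mean 87.6 and SD 22.8 (Section 10.1, Table 1). Both score rules were applied, and the other components were set independently so that CCS = 88%. The correlation ρ between baseline and Month 24 is **an assumption**, because the documents give none. Adjustment multiplies the variance in step 2 by (1 − R²).

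| Assumed ρ | R² | Bound, 196/98 (points) | Power, 196/98 | Power, 196/77 |
|---|---|---|---|---|
| 0 | 0.06% | 6.61 | 80.0% | 74.0% |
| 0.2 | 0.36% | 6.60 | 80.1% | 74.1% |
| 0.3 | 1.0% | 6.58 | 80.4% | 74.4% |
| 0.5 | 3.9% | 6.48 | 81.4% | 75.5% |

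Example at ρ = 0.5, 196/98: SE = 0.0402 × √(1 − 0.0395) = 0.0394; 0.10/0.0394 − 1.645 = 0.893; Φ = 0.814. In patients, 294 × 0.0103 is about 3 at ρ = 0.3, and 294 × 0.0395 is about 12 at ρ = 0.5. These R² values allow any shape of relation with baseline. A straight-line term recovers slightly less (0.9% and 3.5%), so the table is mildly generous.

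**5. Cost of a larger model.** Expected failures are 0.12 × 294 = 35 at 196/98 and 0.12 × 273 = 33 at 196/77. In simulated trials at 196/98, a model with baseline only changed the SE of the risk difference by about 0%, 0% and −2% at ρ = 0.2, 0.3 and 0.5. Adding diagnosis, age and sex, assumed not prognostic, widened the SE by about 1% at 0.2 and 0.3 and narrowed it by only about 1% at 0.5.

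**The case against.** **The unadjusted test is not wrong.** It is valid under randomisation, it estimates the quantity the hypothesis names, and the sample size matches it. This stands. A reader might infer that the planned bound is materially too wide or the analysis deficient; the documents do not support that.

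**Being part of the endpoint does not make baseline a strong predictor.** This also stands. Step 3 shows that the 54-point threshold nearly always supersedes the 10-point rule. Any useful gain comes from the assumed correlation, not from the endpoint's construction.

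**A larger gain is tempting on other assumptions.** A lower Month 24 score, for example 76 ± 20, would put more patients near the thresholds. The documents report 87.6 ± 22.8. Under 76 ± 20 only about 84% would pass the score rules, and with about 5.4% failing on other components CCS would be near 79%, against the 88% used for sizing. Such a case cannot be combined with the 88% variance.

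**More covariates might help.** The documents do not show that diagnosis, age or sex predicts CCS, and the score is already normalised for age and sex (Section 6.7.2, Table 7). With about 35 failures, step 5 argues for a small model.

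**Imbalance is already anticipated.** Section 10.5.1 does name the baseline shoulder assessment. But its trigger, scale and missing consequence remain as described, and an odds-ratio screen does not settle a risk-difference bound.

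**The change needs an amendment.** Section 8.16 requires FDA and IRB approval. That is a real step, but it concerns analysis text only.

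**Conclusion.** The point holds as an optional improvement. The plan leaves a complete baseline measurement unused in its primary comparison and makes adjustment depend on what the data show, on a scale other than the margin's.

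The precision gain is essentially nil at correlations of 0.2 or below, about 0.4 power points at 0.3 and about 1.4 at 0.5. At 196/98 the bound moves by 0.03 to 0.13 points out of 6.61 over correlations of 0.3 to 0.5. For comparison, stopping controls at 77 costs 6.0 power points (80.0% to 74.0%). These figures rest on normal score distributions with the documents' means and SDs, CCS of 88% in both arms, other components independent of baseline, and the assumed correlation.

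The stronger reason to act is procedural: one fixed analysis on the risk-difference scale replaces an open-ended rule.

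**What to change.** **Sections 10.2 and 10.4.** Make the primary estimate the risk difference standardised over the Per Protocol cohort. Fit a logistic model for CCS with arm and baseline Adjusted Constant Score only. Average the predicted success probabilities over all cohort members, first with arm set to Eclipse and then to Univers II, and take the difference. Obtain a one-sided 95% bound by the delta method or bootstrap and compare it with -0.10. Report the unadjusted difference and its bound beside it. The sample size can stay as it is.

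**Section 10.5.1.** Judge any further covariate by its effect on the risk-difference bound and on whether that bound stays above -0.10, in place of the 15% odds-ratio criterion. State what is reported if the conclusion changes.

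**Cost.** A few lines of text and standard code; no new data, visits or patients. The analysis section is part of the protocol, so the change needs the approvals in Section 8.16. It should be settled before CCS is compared between arms.
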